1.3 SCHEDULE OF ACTIVITIES (SOA)

u

Procedures	Screening Day -7 to -1	Enrollment/Baseline Visit 1, Day 1	Study Visit 2 Day 7 +/-1 day	Study Visit 3 Day 14 +/-1 day	Final Study Visit 13 Day 84 +/-1 day
Informed consent	X				
Demographics	X				
Medical history	X				
Randomization	X				
Administer study intervention		X			
Concomitant medication review	X	X----- -----X			
Bcva	X	X	x	x	X
Slit lamp biomicroscopy	X	x	x	x	x
IOP	X	X	x	X	X
Corneal fluorescein stain	X	X		X	X
Conjunctival liissamine stain	X	X		X	X
	X	X		X	X
anesthetized schirmer	X	X		x	x
Dilated ophthalmoscopy	X				x
Training on study medications	X				
Dispense study meds					
\	X				

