5 STUDY POPULATION

5.1 INCLUSION CRITERIA

In order to be eligible to participate in this study, an individual must meet all of the following criteria:

1. Provision of signed and dated informed consent form and HIPPA authorization.
2. Stated willingness to comply with all study procedures and availability for the duration of the study
3. Male or female, aged 18 and older.
4. Diagnosed with moderate to severe dry eye in one or both eyes.
5. History of persistent symptoms despite use of artificial tears and one or more of the following ophthalmic drops: loteprednol, cyclosporine or lifitegrast.
6. At least 40 mm on the ocular discomfort scale.
7. At least 5 spk on one or both corneas.

8. A grade of 1 or greater in the nasal or temporal areas of one or both eyes.
9. Have normal lid anatomy.
10. Ability to take subcutaneous injected medication and be willing to adhere to the study regimen
11. For females of reproductive potential: use of highly effective contraception for at least 1 month prior to screening and agreement to use such a method during study participation and for an additional 4 weeks after the end of Acthar administration
12. For males of reproductive potential: use of condoms or other methods to ensure effective contraception with partner
13. Are postmenopausal (no menstrual cycle for at least one year prior to Visit 1) or have undergone bilateral tubal ligation, hysterectomy, hysterectomy with uni or bilateral oophorectomy, or bilateral oophorectomy.

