8 STUDY ASSESSMENTS AND PROCEDURES

8.1 EFFICACY ASSESSMENTS

List and describe all study procedures and evaluations to be done as part of the study to support the determination of efficacy, as per the primary and secondary objectives outlined in this protocol. Discuss the sequence of events that should occur during the screening process and any decision points regarding participant eligibility. Include the time frame prior to enrollment within which screening procedures/evaluations must be performed (e.g., within 28 days prior to enrollment).

In addition, indicate where appropriate, that procedures/evaluations will be performed by qualified personnel.

- *Once enrolled, initial study visit will occur within one week and can occur on the same day. Study assessments on each study day will occur in this order:*
- ***Subject rated assessment of ocular discomfort by visual analog scale. Subjects will be asked to subjectively rate their eye dryness at Visit 1,2, and 3. Subjects will be instructed to rate eye dryness using the scale below. The total length of the line from “no dryness” to “maximal dryness” is 100 mm. The length of the line between the “no dryness” starting point and the first point at which the subject mark crosses the line will be measured in mm. This assessment is a general assessment of both eyes.***

Instantaneous Evaluation of Eye Dryness

Please place a single line across the line below to indicate the severity of your eye dryness at the present time:

No dryness _____ Maximal dryness _____

- ***Significant non-ocular and significant ocular medical history***
- ***Concomitant medication usage and significant medications taken 6 months prior to screening***
- ***Inclusion/Exclusion criteria***
- ***Urine pregnancy test if required***
- ***BCVA Subjects will be placed at the predetermined mark for ETDRS testing***
- ***. LogMAR will be assessed with ETDRS or modified ETDRS charts and with subjects own corrective lenses or BCVA measured in office whichever is better. Scores are recorded according to ETDRS protocol and right eyes tested first.***
- ***Slit lamp biomicroscopy – 8 mm x 2 mm slit lamp beam will be used right to left and left to right to examine thoroughly the structures of the anterior segment: lids, lashes, conjunctiva, corea, iris, anterior chamber, and lens. Results will be recorded as normal or abnormal. Abnormal findings will be followed by explanation of pathology.***

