9.4.2 ANALYSIS OF THE PRIMARY EFFICACY ENDPOINT(S)

For each primary endpoint:

The improvement of patient comfort as measured by the dry eye comfort questionnaire OSDI defined as the mark listed in mm by the patient describing sensation of dryness. It will be measured at each study visit and reported as an ordinal endpoint. Descriptive statistics will be used for intent to treat patients and safety populations who receive at least one dose of the study drug.

- *The improvement of corneal staining after fluorescein instillation in which discrete superficial punctate stains are counted.. Descriptive statistics will be used for intent to treat patients and safety populations who receive at least one dose of the study drug.*
- *Missing data will be handled by imputation. Outliers will be evaluated by the primary investigator. Subjects who are nonadherent will be referred for re-training and those lost to follow up will be contacted by the study coordinator at least 3 times by phone and ultimately with certified letter if telephone contacts are unsuccessful.*

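### Followed literally, section 8.1 makes one Visit 1 dryness mark both the 40 mm entry test and the baseline, so regression to the mean could count as improvement

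*Protocol*

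**What the plan says.** **Entry.** Protocol 5.1 requires "At least 40 mm on the ocular discomfort scale" and names no visit for the qualifying reading. Section 5.3 allows people who fail on OSDI score to be rescreened and sets no limit.

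**Endpoint.** Section 9.4.2 describes a primary endpoint as the "dry eye comfort questionnaire OSDI defined as the mark listed in mm by the patient describing sensation of dryness" and adds: "It will be measured at each study visit and reported as an ordinal endpoint". Elsewhere (1.1, 3, 10.3) OSDI is a questionnaire or index.

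**Contrast.** Section 9.1 and the SAP use change from baseline to final visit. The SAP applies a two-tailed t test with 95% confidence intervals. Neither says which reading is baseline. There is no control (6.3).

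**Timing in 8.1.** "Subjects will be asked to subjectively rate their eye dryness at Visit 1,2, and 3". The mark comes first in one ordered list that covers every study day, and the inclusion/exclusion check comes later in that list. Section 8.1 also says: "Once enrolled, initial study visit will occur within one week and can occur on the same day".

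**Timing in the Schedule (1.3).** The columns include "Screening Day -7 to -1", "Enrollment/Baseline Visit 1, Day 1" and "Final Study Visit 13 Day 84 +/-1 day". In the text available for this review, one row has no label. It is marked at Screening, Visit 1, Visit 3 and the final visit, the same pattern as the two stains.

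**The concern.** People admitted because one reading was high will, on average, read lower next time without treatment, since part of the high reading was chance. If that same reading is the baseline, the fall appears as improvement. A control arm would show the same fall and cancel it, but this study has none.

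At stake are the mean symptom change and its p-value, in a study that 4.2 says may become the basis for a larger randomised trial. Taking the baseline from a fresh reading removes much of the problem at almost no cost, but the rule has to be set before data are seen.

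**Working it through.** **Reading the passages together**

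1. Section 8.1 is the only place that names visits for the mm mark, and it names Visits 1, 2 and 3. The Schedule calls Visit 1 Enrollment/Baseline. Since 8.1 puts the eligibility check after the mark, following it alone gives one Visit 1 reading that does both jobs.
2. The 8.1 list is not reliable. It omits the final visit, which the endpoint needs. It conflicts with 9.4.2 (every study visit) and with 7.1, which collects a dryness rating at discontinuation.
3. The Schedule separates Screening from Day 1 Baseline. Section 5.3 treats the score as a reason for screen failure, which implies a score at screening. The unlabelled row may be that score.
4. No passage bars the qualifying mark from being the baseline, and none says that it will be.

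**Size, if the qualifying mark is the baseline**

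The plan has no figure to reproduce: 9.2 gives 12 participants with no SD, effect size or power.

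Inputs from the documents: 40 mm cut (5.1), n = 12 (9.2), and 25 screenings for 12 enrolled (5.4), so 25 − 12 = 13 failures for all reasons.

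Assumptions: normal scores, SD 20 mm, correlation r between readings of 0.5 to 0.8, no drug effect, no rescreening, 0 and 100 mm limits ignored, and two-sided alpha 0.05 (inferred from the 95% intervals). A false significant improvement is then nominally 2.5%.

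With pass fraction p and k the standard normal point that has p above it:

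expected spurious improvement = (1 − r) × SD × φ(k) / p

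Example, 3 failures on this score: p = 22/25 = 0.88 and φ(k)/p = 0.227. For r = 0.5, 0.5 × 20 × 0.227 = 2.27 mm. For r = 0.8, 0.2 × 20 × 0.227 = 0.91 mm.

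The false-improvement rates come from simulating 60,000 groups of 12 with a paired t test.

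| Failures on this score | p | φ(k)/p | Shift, r 0.8 to 0.5 | False improvement, r 0.8 to 0.5 |
|---|---|---|---|---|
| 1 | 0.96 | 0.090 | 0.36 to 0.90 mm | about 3% |
| 3 | 0.88 | 0.227 | 0.91 to 2.27 mm | about 4% to 6% |
| 6.5 (half of 13) | 0.74 | 0.438 | 1.75 to 4.38 mm | about 6.5% to 11% |
| 13 (upper bound) | 0.48 | 0.830 | 3.32 to 8.30 mm | 13.5% to 30% |

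The mm figures scale with SD. For a given pass fraction and r, the percentages do not depend on SD. Rescreening would add to the shift. The amount is not estimated for this plan, because the number of rescreens, and whether 25 counts people or attempts, are not stated.

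**Size with a separate Day 1 baseline (p = 0.74)**

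If screening correlates r1 with Day 1 and r2 with Day 84, the remaining shift is (r1 − r2) × SD × φ(k)/p:

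- r1 = r2: 0 mm, about 2.5% false improvement.
- 0.7 and 0.5: 0.2 × 20 × 0.438 = 1.8 of 4.4 mm remains (4.6%).
- 0.85 and 0.5: 0.35 × 20 × 0.438 = 3.1 of 4.4 mm remains (7.3%).
- 0.9 and 0.8: 0.1 × 20 × 0.438 = 0.9 of 1.8 mm remains (4.2%).

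**Could the screening-to-Day-1 change reveal the bias?** At r1 = 0.85 its expected value is 0.15 × 20 × 0.438 = 1.3 mm. Its standard error is about 20 × √(2 × 0.15 / 12) = 3.2 mm. It could not.

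**The case against.** The strongest reply is that the Schedule already has the right structure. It heads Day 1 as Baseline and ends Screening the day before. Section 5.3 makes sense only if a score exists at screening. Corneal staining, which also has an entry cut in 5.1, is marked at both Screening and Visit 1, so qualifying first and re-measuring at baseline looks like the intended pattern. The blank row label may have been lost in converting the file and is not counted here as a defect. All of this stands, and it makes a separate Day 1 baseline a plausible intention. It does not settle the matter, because 8.1 still omits Screening for this mark and neither 9.1 nor the SAP ties baseline to Day 1.

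A reader might infer from the same-day sentence in 8.1 that screening and Visit 1 may be merged. That sentence runs from enrolment, not from screening, and its one-week limit matching the screening window is only suggestive.

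It is also fair that the harm depends on the endpoint being the mm mark. If OSDI means the questionnaire, the 40 mm cut does not select on it directly. Finally, this is an unpowered pilot, 9.4.2 plans descriptive statistics for this endpoint, no decision rests on the p-value, and 4.2 already names the lack of control and the variable disease. These points lower the priority. They do not make a biased mean change harmless.

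**Conclusion.** The point holds as a conflict between passages, one reading of which biases the result. Section 8.1 taken literally uses the Visit 1 mark for both entry and baseline and names no final-visit mark. The Schedule, 5.3 and 9.4.2 suggest otherwise.

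Two stronger claims are not supported. One is that the plan has decided to use the qualifying mark as baseline: no passage says so. The other is that the false-improvement rate is 30%: that needs all 13 failures to fall on this one score, although 5.1 and 5.2 list 13 inclusion and 10 exclusion criteria, and it also needs the lowest assumed correlation.

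A reasonable statement of size is 0.4 to 4.4 mm, with about 3% to 11% false improvement against 2.5%. It is conditional on the mm mark being the endpoint, the qualifying mark being the baseline, SD 20 mm, r 0.5 to 0.8, and between 1 and half of the failures being on this score. The SD, the correlation and the failure share are assumptions, and the effect could be negligible. The change is worth making, at modest priority.

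**What to change.** - Reconcile 8.1 with the Schedule so that the mm mark is taken at Screening (for eligibility only), on Day 1 before dosing, and at the final visit. Make sure the Schedule row for it is labelled.
- State in 9.1 and the SAP that baseline is the Day 1 mark and that this mark is not used for eligibility.
- Reconcile which score OSDI means in 5.3 and 9.4.2, and keep every screening score, including those from rescreening.

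The cost is a few sentences and at most one extra visual analogue scale per person screened. Same-day screening and Visit 1 would be lost, if that was intended; the Schedule already provides for both visits.

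The change reduces the bias. Some remains if readings taken days apart agree better than readings 12 weeks apart, and placebo response is untouched. At n = 12 the screening-to-Day-1 change should not be presented as a test of whether the bias is present.

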8.2 SAFETY AND OTHER ASSESSMENTS

- **BCVA Subjects will be placed at the predetermined mark for ETDRS testing**
- **LogMAR will be assessed with ETDRS or modified ETDRS charts and with subjects own corrective lenses or BCVA measured in office whichever is better. Scores are recorded according to ETDRS protocol and right eyes tested first.**
- **Slit lamp biomicroscopy – 8 mm x 2 mm slit lamp beam will be used right to left and left to right to examine thoroughly the structures of the anterior segment: lids, lashes, conjunctiva, cornea, iris, anterior chamber, and lens. Results will be recorded as normal or abnormal. Abnormal findings will be followed by explanation of pathology.**
- **IOP measurements will be performed using Goldman applanation tonometry according to the investigators standard protocol. All pressures will be recorded in mm Hg. IOP will be measured at each time point and at the investigator's discretion.**
- **Dilated ophthalmoscopy will occur at the first and last study visit and include assessment of the optic nerve head for pallor and cupping.**

Adverse events will be collected at each time point

h

8.3 ADVERSE EVENTS AND SERIOUS ADVERSE EVENTS

8.3.1 DEFINITION OF ADVERSE EVENTS (AE)

Adverse event means any untoward medical occurrence associated with the use of an intervention in humans, whether or not considered intervention-related (21 CFR 312.3)

8.3.2 DEFINITION OF SERIOUS ADVERSE EVENTS (SAE)

An adverse event (AE) or suspected adverse reaction is considered "serious" if, in the view of either the investigator or sponsor, it results in any of the following outcomes: death, a life-threatening adverse event, inpatient hospitalization or prolongation of existing hospitalization, a persistent or significant incapacity or substantial disruption of the ability to conduct normal life functions, or a congenital anomaly/birth defect. Important medical events that may not result in death, be life-threatening, or require hospitalization may be considered serious when, based upon appropriate medical judgment, they may jeopardize the participant and may require medical or surgical intervention to prevent one of the outcomes listed in this definition. Examples of such medical events include allergic bronchospasm requiring intensive treatment in an emergency room or at home, blood dyscrasias or convulsions that do not result in inpatient hospitalization, or the development of drug dependency or drug abuse.

8.3.3 CLASSIFICATION OF AN ADVERSE EVENT

8.3.3.1 SEVERITY OF EVENT

For adverse events (AEs) not included in the protocol defined grading system, the following guidelines will be used to describe severity.

- **Mild** – Events require minimal or no treatment and do not interfere with the participant's daily activities.
- **Moderate** – Events result in a low level of inconvenience or concern with the therapeutic measures. Moderate events may cause some interference with functioning.
- **Severe** – Events interrupt a participant's usual daily activity and may require systemic drug therapy or other treatment. Severe events are usually potentially life-threatening or incapacitating. Of note, the term "severe" does not necessarily equate to "serious".

8.3.3.2 RELATIONSHIP TO STUDY INTERVENTION

All adverse events (AEs) must have their relationship to study intervention assessed by the clinician who examines and evaluates the participant based on temporal relationship and his/her clinical judgment. The degree of certainty about causality will be graded using the categories below. In a clinical trial, the study product must always be suspect.

- **Related** – The AE is known to occur with the study intervention, there is a reasonable possibility that the study intervention caused the AE, or there is a temporal relationship between the study intervention and event. Reasonable possibility means that there is evidence to suggest a causal relationship between the study intervention and the AE.
- **Not Related** – There is not a reasonable possibility that the administration of the study intervention caused the event, there is no temporal relationship between the study intervention and event onset, or an alternate etiology has been established.

OR

- **Definitely Related** – There is clear evidence to suggest a causal relationship, and other possible contributing factors can be ruled out. The clinical event, including an abnormal laboratory test

result, occurs in a plausible time relationship to study intervention administration and cannot be explained by concurrent disease or other drugs or chemicals. The response to withdrawal of the study intervention (dechallenge) should be clinically plausible. The event must be pharmacologically or phenomenologically definitive, with use of a satisfactory rechallenge procedure if necessary.

- **Probably Related** – There is evidence to suggest a causal relationship, and the influence of other factors is unlikely. The clinical event, including an abnormal laboratory test result, occurs within a reasonable time after administration of the study intervention, is unlikely to be attributed to concurrent disease or other drugs or chemicals, and follows a clinically reasonable response on withdrawal (dechallenge). Rechallenge information is not required to fulfill this definition.
- **Potentially Related** – There is some evidence to suggest a causal relationship (e.g., the event occurred within a reasonable time after administration of the trial medication). However, other factors may have contributed to the event (e.g., the participant's clinical condition, other concomitant events). Although an AE may rate only as "possibly related" soon after discovery, it can be flagged as requiring more information and later be upgraded to "probably related" or "definitely related", as appropriate.
- **Unlikely to be related** – A clinical event, including an abnormal laboratory test result, whose temporal relationship to study intervention administration makes a causal relationship improbable (e.g., the event did not occur within a reasonable time after administration of the study intervention) and in which other drugs or chemicals or underlying disease provides plausible explanations (e.g., the participant's clinical condition, other concomitant treatments).
- **Not Related** – The AE is completely independent of study intervention administration, and/or evidence exists that the event is definitely related to another etiology. There must be an alternative, definitive etiology documented by the clinician.

8.3.3.3 EXPECTEDNESS

The primary investigator will be responsible for determining whether an adverse event (AE) is expected or unexpected. An AE will be considered unexpected if the nature, severity, or frequency of the event is not consistent with the risk information previously described for the study intervention.

8.3.4 TIME PERIOD AND FREQUENCY FOR EVENT ASSESSMENT AND FOLLOW-UP

Describe how AEs and SAEs will be identified and followed until resolved or considered stable. Specify

The occurrence of an adverse event (AE) or serious adverse event (SAE) may come to the attention of study personnel during study visits and interviews of a study participant presenting for medical care, or upon review by a study monitor.

All AEs including local and systemic reactions not meeting the criteria for SAEs will be captured on the appropriate case report form (CRF). Information to be collected includes event description, time of onset, clinician's assessment of severity, relationship to study product (assessed only by those with the training and authority to make a diagnosis), and time of resolution/stabilization of the event. All AEs occurring while on study must be documented appropriately regardless of relationship. All AEs will be followed to adequate resolution.

Any medical condition that is present at the time that the participant is screened will be considered as baseline and not reported as an AE. However, if the study participant's condition deteriorates at any time during the study, it will be recorded as an AE.

Changes in the severity of an AE will be documented to allow an assessment of the duration of the event at each level of severity to be performed. AEs characterized as intermittent require documentation of onset and duration of each episode.

The study coordinator will record all reportable events with start dates occurring any time after informed consent is obtained until 7 (for non-serious AEs) or 30 days (for SAEs) after the last day of study participation. At each study visit, the study coordinator will inquire about the occurrence of AE/SAEs since the last visit. Events will be followed for outcome information until resolution or stabilization.

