4 STUDY DESIGN

4.1 OVERALL DESIGN

- The hypothesis is that use of H.P. Acthar gel subcutaneously has the ability to reduce ocular surface inflammation in moderate to severe dry eye and improve the signs and symptoms over the course of the trial.*
- Single site pilot study Pilot study*

- *H.P. Acthar gel will be dosed two or three times weekly to control signs and symptoms at the discretion of the primary investigator.*
- *One study arm of active intervention for up to 89 days*
- *Single site*
- *Study intervention is use of H.P. Acthar Gel)*
- *No interim analysis is planned*

There are no planned stratifications.

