4.4 END OF STUDY DEFINITION

A participant is considered to have completed the study if he or she has completed all phases of the study including the last visit or the last scheduled procedure shown in the Schedule of Activities (SoA), Section 1.3.

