5.4 STRATEGIES FOR RECRUITMENT AND RETENTION

Anticipate 25 screenings for 12 enrolled subjects.

- *One site in the US.*
- *Source of participants will be outpatient clinics and general public*
- *Potential participants will be identified and approached by chart review, during regular dry eye clinic visits and self-identified by general dry eye study signs within our clinics*

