6.1.2 DOSING AND ADMINISTRATION

Each participant will be started at 80 IU subcutaneously 2-3 weekly and the dosing increased to up to three times weekly at the discretion of the primary investigator. The dosing will remain consistent unless the investigator decides to reduce or escalate the dosing at the one month mark. The dosing may be stopped altogether and the subject followed only for safety in the event of uncontrolled hypertension, blood sugar, glaucoma or other serious adverse events in the opinion of the investigator. The dosing of study drug will continue for 12 weeks.

Missed or delayed doses should be taken as soon as realized unless it would result in two doses being given at once, in which case the investigator should be contacted for a modified dosing schedule.

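### The plan records adverse events for 7 days and serious ones for 30 days after participation, but schedules no contact in either window for completers or full withdrawals

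*Protocol*

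**What the plan says.** Protocol section 8.3.4 makes the study coordinator record events that start at any time from consent "until 7 (for non-serious AEs) or 30 days (for SAEs) after the last day of study participation". The active means it gives is enquiry at visits: "At each study visit, the study coordinator will inquire about the occurrence of AE/SAEs since the last visit". Section 8.2 likewise ties adverse event (AE) collection to the study time points. Besides visits, section 8.3.4 says events may reach staff through "interviews of a study participant presenting for medical care, or upon review by a study monitor".

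The last column of the Schedule of Activities (section 1.3) is "Final Study Visit 13 Day 84 +/-1 day". Section 4.4 counts a participant as a completer once he or she has "completed all phases of the study including the last visit or the last scheduled procedure shown in the Schedule of Activities".

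On treatment length, sections 4.3 and 6.1.2 give 12 weeks, while section 4.1 has "One study arm of active intervention for up to 89 days". Section 6.1.2 also provides for stopping drug while staying in the study: "The dosing may be stopped altogether and the subject followed only for safety". Section 7.1 keeps such participants on their remaining study procedures.

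Section 8.3.6 requires the clinician to report every serious adverse event (SAE) to the sponsor immediately, whatever its cause.

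**The concern.** The plan sets a recording duty for a period in which it gives the site no scheduled occasion to ask. Immediate reporting under section 8.3.6 can work only for SAEs that the site hears about. If the plan is followed to the letter, an SAE two weeks after the final visit may never be recorded, and no deviation will have occurred. The data would also not distinguish a participant who had no event from one who was never asked.

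The timing matters here. Dosing runs for 12 weeks, so the unasked period begins directly after the last injections. The risks listed in section 2.3.1 include infection, bleeding stomach ulcers and loss of diabetic control. The contraception criterion in section 5.1 runs for four weeks after the last dose, so the protocol itself treats that period as relevant to risk. Safety is a stated objective in sections 1.1 and 3.

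A smaller point compounds this: the day from which the windows are counted is not defined. Section 4.4 supports the final visit for completers, but under the 89-day limit in section 4.1 a dose could follow that visit.

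**Working it through.** The plan gives no figure to reproduce. The check is calendar arithmetic set against the schedule, then a review of each route by which an event could become known.

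**Inputs.** Final visit on Day 84 ± 1, so Day 83 to 85 (section 1.3). Windows of 7 and 30 days (section 8.3.4). Intervention limit of 89 days (section 4.1), taken to run from Day 1. Twelve participants completing (section 9.2).

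**Windows counted from the final visit.**
- Non-serious AEs: 83 + 7 = 90 and 85 + 7 = 92, so they close on Days 90 to 92.
- SAEs: 83 + 30 = 113 and 85 + 30 = 115, so they close on Days 113 to 115.
- Scheduled contacts in either window: 0.
- For a Day 84 final visit, the 30 unasked days are 30/114 = 26% of the Day 1 to 114 SAE recording period.

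**Windows counted from a last dose on Day 89.**
- Close on 89 + 7 = Day 96 and 89 + 30 = Day 119.
- The SAE window then closes 119 − 85 = 34 to 119 − 83 = 36 days after the last scheduled enquiry.
- Scheduled contacts: again 0.

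**Routes that might fill the gap.**

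| Route | Section | Active enquiry in the windows? |
|---|---|---|
| Enquiry at study visits | 8.2, 8.3.4 | No; visits have ended |
| Participant presents for care | 8.3.4 | Passive |
| Monitor review | 8.3.4, 10.1.7 | One on-site check of a random part of the data, by the primary investigator |
| Follow-up of AEs and SAEs to resolution or stability | 8.3.4, 8.3.6 | Known events only |
| Pregnancy follow-up | 8.3.9 | Known pregnancies only |
| Calls and letter after a missed visit | 7.3 | No visit remains to be missed after the final one; not an AE enquiry |
| Assessments at discontinuation | 7.1 | Done when drug is stopped, not afterwards |

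Section 7.2 requires the reason for a full withdrawal to be recorded but schedules no later contact. Participants who stop drug and stay in the study are a different case: their remaining visits give them off-drug enquiry.

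**Scale only.** The documents give no SAE rate. If each of 12 participants had an assumed risk p of an SAE in the 30 days, the chance that at least one occurs is 1 − (1 − p)^12: 11% for p = 1%, 22% for 2%, 46% for 5% and 72% for 10%. These are chances that an SAE occurs, not that it is missed. One participant is 1/12 = 8.3% of the sample.

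**The case against.** The strongest reply is that passive capture after the last visit is the method the plan states, not a contradiction in it. Section 8.3.4 names the routes, and events open at exit are followed up. Some participants are the site's own patients, found "during regular dry eye clinic visits and self-identified by general dry eye study signs within our clinics", and may well return. This stands as a reason to expect that some events will be caught. It does not supply a scheduled enquiry, and it offers nothing dependable for a participant who leaves without an open event.

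A second reply concerns participants who simply stop attending. Section 7.3 requires an attempt to reach them within 72 hours, then, where possible, three calls and, if necessary, a certified letter. Depending on how the last day is defined, these attempts could fall inside the SAE window. That is a fair qualification. But the attempts are meant to restore attendance, are not described as AE enquiries, and have by definition failed for anyone finally deemed lost.

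Third, the Day 119 figure depends on section 4.1, while sections 4.3 and 6.1.2 say 12 weeks. This is correct, and the Day 89 case should be read only as the alternative anchor. The gap is there without it.

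Fourth, the practical effect is limited. Section 9.4.4 summarises events during treatment, no efficacy analysis is touched, and this is a 12-person pilot. That limits the weight of the point but does not remove the duty to report SAEs.

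Finally, the consent pages and the schema figure are not available, and the schedule table is partly broken. An instruction in the consent form to report later events would reduce the risk but would still be passive. The last readable column of the schedule is labelled as the final visit.

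**Conclusion.** The concern holds. For completers and for treated participants who withdraw fully, the plan's 7-day and 30-day windows contain no scheduled enquiry, so capture there is passive and reportable SAEs may be missed. For completers, counted from the final visit, the SAE window runs unasked to Days 113 to 115; on the alternative last-dose anchor it runs to Day 119. The number of events missed is unknown.

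The conclusion assumes that the missing or broken parts of the schedule contain no contact after the final visit, which its last column heading supports. The effect is confined to SAE capture and reporting. The change is worth making because it is cheap and serves a stated safety objective, not because any planned result would otherwise be wrong.

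**What to change.** 1. In section 8.3.4, define the start of both windows as the later of the last visit and the last dose. Keep the 7 and 30 days as they are.
2. Add one column to the Schedule of Activities: a coordinator telephone contact about 30 days after that date, for every treated participant, including withdrawals who agree to be contacted. The call asks about SAEs over the 30 days and non-serious AEs over the first 7.
3. Record a participant who was asked and reported nothing separately from one who could not be reached.
4. Optionally, add a call at 7 days to reduce recall error for non-serious AEs.

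**Cost.** One definition and one schedule column, or two with the optional call. With w treated withdrawals who agree to contact, and whom section 7.2 says are replaced, the number of calls is 12 + w, or 24 + 2w with the optional call. The documents do not give w; an assumed range of 0 to 4 gives 12 to 16 calls, or 24 to 32. The existing coordinator can make them. The downsides are some recall error for non-serious AEs if only the 30-day call is made, and possibly a few more events to report.
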